9.5.3 Analyses of Other PK Endpoint(s)

PK concentrations during the Lead-in Period will be summarized descriptively by visit based on the LTS. Boxplots of serum concentration over time during Lead-in Period will be presented graphically using the LTS.

PK concentrations between Week 28 and 30 will be summarized descriptively by nominal visit and actual treatment group based on the PK Concentration Analysis Set. Individual and mean (+/- STD) serum concentration time-profiles between Week 28 and 30 by actual treatment group will be presented graphically on semilogarithmic and linear scales using the PK Concentration Analysis Set.

t_{last} of ABP 501 and Humira between weeks 28 and 30 will be listed by subject and by treatment group using PK Parameter Analysis Set.

9.5.4 Subgroup Analyses

The primary PK endpoints will be summarized and compared within the neutralizing ADA negative subgroup for the PK Parameter Analysis Set and employing the analysis methods described in Section 9.5.1.1.

9.6 Efficacy Analyses

9.6.1 Analyses of Primary Efficacy Endpoint(s)

None.

9.6.2 Analyses of Secondary Efficacy Endpoint(s)

9.6.2.1 Primary Analysis

The primary analysis will be performed based on the Per-protocol Efficacy Analysis Set according to the actual treatment groups with missing PASI score at Week 30 visit imputed by LOCF and missing PASI 75, PASI 90 and PASI 100 response at week 30 imputed by NRI. Confidence interval for response rates will be calculated by the Clopper-Pearson method.

The point estimate and 90% CI of the mean difference in PASI percent improvement from baseline at Week 30 will be estimated from an ANCOVA model adjusting for the baseline PASI value and the stratification factors.

Protocol Number: 20200497

Date: 10FEB2023 Page 30 of 36

The point estimate and 90% CI of the risk difference in PASI 75, PASI 90, and PASI 100 response rates at Week 30 will be estimated from a generalized linear model with an identity link adjusting for the stratification factors.

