1.3 Schedule of Assessments

Table 1-1. Schedule of Assessments

									We	ek													
	Screen	Baseline	(+ 3 days) (± 3 days)											PK Endpoint Assessments Post Actual Week 28 Dose Date							End of Study (± 3 days) ^a		
Study Visit	≤ 28 days	Week 1/D ay 1	W2/ Day 8	4	6	8	10	12 ^j	14	16	18	20	22	24	26	28 ^b	+1d	+3d	+4d	+7d	+11d	+14d	32
Informed consent	Χ																						
Medical/medication history	Χ																						
Physical examination	Х	Χ																					Х
Height	Χ																						
Weight	Χ	Χ																					Х
Vital signs	Χ	Χ	Χ		Х			Χ		Х		Х				Х						Χ	Х
Adverse events	Xc	Χ	Χ	Х	Х	Χ	Х	Χ	Χ	Х	Χ	Х	Х	Х	Х	Х	Χ	Χ	Х	Χ	Χ	Χ	Х
Concomitant meds	Х	Χ	Х	Х	Х	Х	Х	Χ	Х	Х	Χ	Х	Х	Х	Х	Х	Χ	Х	Х	Χ	Х	Χ	Х
Disease assessments																							
PASI/sPGA/affected BSA	Χ	Χ			Χ			\mathbf{X}^{j}		Х		Χ										Χ	
Laboratory assessments																							
TB Testing ^d	Χ																						
Chest radiography ^e	Χ																						
TB worksheet ^f	Χ																						
Serology (HBsAg, HBcAb, HCV, HIV)	Х																						
Serum pregnancy test	Х																						
Urine pregnancy test		Χ			Х			Χ				Х				Х							Х
Hematology	Χ	Χ			Х			Χ				Х											Х
Chemistry	Х	Χ			Х			Χ				Х											Х
Urinalysis	Х	Χ																					Х
Pharmacokinetic sample ^h		Х			Х			Χ		Х		Χ				Χg	Χ	Χ	Χ	Χ	Χ	Χ	Х
Antidrug antibody sample ^h		Χ			Х			Χ		Х		Χ				Х						Χ	Х
Investigational product																							
Randomization								Χ															
IP administration ⁱ		Χ	Χ	Χ	Х	Х	Х	Χ	Χ	Х	Χ	Х	Х	Χ	Х	Χ							

Clinical Study Protocol: 20200497

Final 1.0 Date: 03 Jun 2021 Page **18** of **87**

BSA = body surface area; CT = computed tomography; HBcAb = hepatitis B core antibody; HBsAg = hepatitis B surface antigen; HCV = hepatitis C virus; HIV = human immunodeficiency virus; IP = investigational product; MRI = magnetic resonance imaging; PASI = Psoriasis Area and Severity Index; PK = pharmacokinetics; PPD = purified protein derivative; sPGA = static Physician's Global Assessment; TB = tuberculosis.

- ^a Subjects terminating early from the study should complete all procedures scheduled for EOS Visit (ie, week 32) within 28 days after withdrawal/discontinuation if possible.
- b Week 28 visit will have a window of ± 3 days.
- ^c Report serious adverse events that occur after signing informed consent form. Nonserious adverse events are reported as medical history prior to enrollment.

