- d A QuantiFERON TB/T-spot or local equivalent will be performed. For the purposes of this study. Additional TB tests could be performed during the course of the study at the discretion of the investigator and according to local practice.
- ^e Chest radiograph will include anterior/posterior or posterior/anterior and lateral views. Historical films obtained or formal reports signed off by radiologist in the 3 months prior to screening are acceptable. Chest X-ray may be substituted by a chest CT or chest MRI, if available within 3 months prior to screening.
- Only for subjects with a positive tuberculosis test (ie, positive or indeterminate QuantiFERON, positive PPD).
- Pharmacokinetic sample will be collected as close to the nominal time points as possible. Study centers should strictly adhere to the tolerance windows outlined in the table below for week 28 through week 30 PK endpoint sample collection.
- h Pharmacokinetic and antidrug antibody samples should be drawn prior to investigational product administration at dosing visits (except 1 hour post week 28 dose pharmacokinetic sample).
- ABP 501 or adalimumab will be administered after all other procedures are completed for each visit. If the subject presents with an infection/adverse event at the dosing visit(s), the administration of investigational product may be delayed up to 5 days. In the case of delayed or missed dose, subsequent doses should be administered according to the original schedule (ie, at the planned time point relative to first dose/day 1). A minimum of 7 days must elapse between administrations of 2 doses.
- Subjects achieving less than PASI 50 response at week 12 visit will be considered non-responders and will be discontinued from the study at week 12. Subjects unable to complete the week 12 visit will be discontinued from the study. These subjects will be asked to complete an End of Study Visit procedures.

Table 1-2. Tolerance Windows for Pharmacokinetic Endpoint Sample Collection

Study Visit	Tolerance Windows ^a	
Week 28 predose	Within 3 hours prior to week 28 investigational product administration	
1 hour post week 28 dose	± 15 minutes	
1 day post week 28 dose	± 5 hours	
3 days post week 28 dose	± 6 hours	
4 days post week 28 dose	± 6 hours	
7 days post week 28 dose	± 6 hours	
11 days post week 28 dose	± 24 hours	
14 days post week 28 dose	± 48 hours	

PK = pharmacokinetic(s).

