Q2W with last dose at week 28. Subjects randomized to the switching group will switch to ABP 501 Q2W at week 12 (dosed week 12 and week 14), then back to adalimumab Q2W at week 16 (dosed week 16 and week 18), and again to ABP 501 Q2W at week 20, (dosed week 20, week 22, week 24, week 26, and with last dose of ABP 501 at week 28).

All enrolled subjects not randomized at week 12 will be considered lead-in failures and the lead-in failure reason will be documented.

An EOS Visit will be conducted at week 32.

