Developing antibody incidence during the Post-randomization Period is defined as the number of subjects in the Safety Analysis Set (SAS) who have a positive result post randomization and have never tested positive (i.e., negative or no results) prior to the first dose of post-randomization IP divided by the number of subjects in the SAS who have at least a result post randomization.

End of Study (EOS) Date

The EOS date is the date recorded on the End of Study page of the CRF.

First Dose Date

It is defined as the date the subject received the first dose of IP.

First Post-randomization Dose Date

It is defined as the date the subject received the first post-randomization dose of IP.

Last Dose Date

It is defined as the date the subject received the last dose of IP.

Last Observation Carried Forward (LOCF)

Protocol Number: 20200497

Date: 10FEB2023 Page 14 of 36

A method of imputation where missing post-baseline data will be imputed by carrying forward the last non-missing post-baseline value for that endpoint. Baseline values will not be carried forward.

Neutralizing ADA Negative Subgroup

Defined as subjects in the subset of Safety Analysis Set (SAS) who have never tested positive (i.e. tested negative or no results) prior to the first dose of post-randomization IP, have at least one neutralizing ADA result post-randomization, and all available post-randomization neutralizing ADA results are negative.

Non Responder Imputation (NRI)

A method of imputation where a subject with missing post-baseline binary response data will be imputed as a non-responder, regardless of the reasons for missing data.

Study Analysis Visit

If more than one actual visit (including the unscheduled visits) falls within the same defined window, the visit closest to the target day with non-missing data will be considered for analysis. If two actual visit dates are at the same distance from the target day, the later visit with non-missing data will be considered for analysis.

For Efficacy, Vital, Safety Lab & PK

					Endpoint	
Study Analysis Visit	Target Day	Study Day	Interval (days)	Efficacy	Vital & Safety Labª	PK
Baseline ^b	1	≤1	NA	Х	Х	Х
Week 2	8	2-21	20		X	
Week 6	36	22-56	35	Χ	X	Χ
Week 12 ^b	78	57-91	35	Χ	X	Χ
Week 16	106	92-119	28	Χ	X	Χ
Week 20	134	120-161	42	Χ	X	Χ
Week 28	190	162-196	35		X	Χ
Week 30	14 days post week 28 dose	197-210	14	Х	Х	
Week 32	218	≥211	NA		Χ	

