9.6.3 Analyses of Other Efficacy Endpoint(s)

The analyses of the other efficacy endpoints in this section will be based on the Perprotocol Efficacy Analysis Set by actual treatment group.

The PASI percent improvement from day 1 at weeks 6, 12, 16 and 20 and the PASI 75, PASI 90 and PASI 100 response rates at weeks 6, 12,16 and 20 will be summarized descriptively by treatment group based on observed data.

BSA absolute values and changes from baseline will be summarized descriptively by visit (at weeks 6, 12, 16, 20 and 30) and treatment group using observed data. In addition, the point estimate and 90% CI of the mean difference in the change from baseline for BSA at Week 30 between the two groups will be estimated from an ANCOVA model adjusting for the baseline BSA value and the stratification factors with missing values imputed by LOCF.

sPGA scores will be summarized descriptively by visit (at weeks 6, 12, 16, 20 and 30) and treatment group. sPGA response (0/1) will also be summarized descriptively by visit and treatment group using observed data. The sPGA response (0/1) at Week 30 will be analyzed by a generalized linear model adjusting for the stratification factors with missing values imputed by NRI. Confidence interval for response rate will be calculated by the Clopper-Pearson method.

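### LOCF for week 30 PASI percent improvement and BSA change normally carries a week 20 value taken before the third switch, so it cannot reflect the final five ABP 501 doses

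*SAP*

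**What the plan says.** **Imputation rule.** The main analysis of PASI percent improvement has "missing PASI score at Week 30 visit imputed by LOCF" (SAP 9.6.2.1). The week 30 BSA model is an ANCOVA "with missing values imputed by LOCF" (SAP 9.6.3). SAP 5.1 defines LOCF as missing data "imputed by carrying forward the last non-missing post-baseline value for that endpoint", and baseline is not carried. PASI 75/90/100 and sPGA response use non-responder imputation instead. Protocol 9.5.2.2 also names LOCF for PASI percent improvement.

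**Assessment schedule.** The row "PASI/sPGA/affected BSA" in Protocol Table 1-1 is marked after randomization at weeks 12, 16 and 20, and then only 14 days after the week 28 dose. It is blank at weeks 22 to 28 and at the week 32 visit. The SAP agrees: its visit-window table has no efficacy entry at week 28 or week 32, and SAP 9.6.3 has BSA "summarized descriptively by visit (at weeks 6, 12, 16, 20 and 30").

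**Treatment sequence.** The switching arm receives ABP 501 at weeks 12 and 14, "then back to adalimumab Q2W at week 16 (dosed week 16 and week 18"), and ABP 501 again at weeks 20, 22, 24, 26 and 28 (Protocol 4.1). A footnote to Table 1-1 says that product "will be administered after all other procedures are completed for each visit", so week 20 PASI and BSA precede the week 20 dose.

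**Analysis set and repeats.** The LOCF analyses use the Per-protocol Efficacy Analysis Set, which admits only subjects given every assigned dose after randomization (SAP 6.5). SAP 9.6.2.2 repeats the SAP 9.6.2.1 models on observed data, in the FAS and in the per-protocol set. SAP 9.6.3 states no such repeat for the week 30 BSA model.

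**The concern.** The design ends with a switch from adalimumab to ABP 501 followed by five ABP 501 doses, and week 30 is where the clinical effect of that block is read. Under the stated rule, a switching subject without a week 30 assessment normally receives a score taken before that block began. If switching caused a late loss of response, the imputed subjects could not show it.

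The ANCOVA would also treat each carried value as if it had been observed at week 30, so the interval takes no account of not knowing what happened over the last ten weeks.

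At stake is how far the main estimates of PASI percent improvement and BSA change can be read as week 30 estimates. The PASI result can be set against its observed-data repeat. The BSA model cannot.

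**Working it through.** The documents give no power, margin or missing-data rate for the efficacy endpoints, so there is no plan figure to reproduce. The steps below establish what is carried, then its size under stated assumptions.

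**1. Gap before week 30.** Target days in SAP 5.1 are 78 (week 12), 106 (week 16) and 134 (week 20). Week 30 is 14 days after the week 28 dose, targeted at day 190, so day 204.
- Gaps: 106 - 78 = 28; 134 - 106 = 28; 204 - 134 = 70 days.
- The last gap is 70 / (204 - 78) = 70/126 = 55.6% of the time from week 12 to week 30.
- If week 20 is also missing, the carried value comes from week 16 or earlier.

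**2. What drug the week 20 value reflects.** Protocol 6.7 gives a terminal half-life of about 14 days. Assume equal two-weekly doses, a double first dose and simple exponential decay, so each dose halves every two weeks.
- At week 20 before dosing, ABP 501 from weeks 14 and 12: 0.125 + 0.0625 = 0.1875.
- Adalimumab from weeks 18 and 16: 0.5 + 0.25 = 0.75, plus about 0.06 from the lead-in.
- ABP 501 share: 0.1875 / (0.1875 + 0.81) = about 19%; adalimumab about 81%.
- The same calculation at week 30 gives about 97% ABP 501.

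**3. Effect on the estimated difference.** Let D20 and D30 be the true arm differences (switching minus continued-use). Let m_S and m_C be the shares missing at week 30, and c_S and c_C the mean changes from week 20 to week 30. Assume that missingness is unrelated to outcome and that the week 20 value is the one carried.
- Expected LOCF difference = D30 - m_S × c_S + m_C × c_C.
- With equal missingness m this becomes (1 - m) × D30 + m × D20.

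*Difference arising wholly after week 20 (D20 = 0).* The shift toward zero is m × D30 in absolute size:
- m = 1%, 5 points: 0.01 × 5 = 0.05 points.
- m = 5%, 10 points: 0.05 × 10 = 0.5 points.

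For an assumed 5-point true difference:

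| m | all after week 20 | simulated | half present at week 20 |
|---|---|---|---|
| 2% | 0.98 × 5 = 4.90 | 4.92 | 4.90 + 0.02 × 2.5 = 4.95 |
| 5% | 0.95 × 5 = 4.75 | 4.74 | 4.75 + 0.05 × 2.5 = 4.875 |
| 15% | 0.85 × 5 = 4.25 | 4.26 | 4.25 + 0.15 × 2.5 = 4.625 |

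The simulation used 145 per arm, an SD of 20 and a week 20 to week 30 correlation of 0.6 (all assumed), with 4,000 replicates. The 15% row borrows the planned post-randomization dropout rate and is an upper case, because subjects who stop before week 28 are not in the per-protocol set.

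*Unequal missingness with no true difference.* Assume both arms improve 5 points after week 20, with m_S = 5% and m_C = 1%. The LOCF difference is 0 - 0.05 × 5 + 0.01 × 5 = -0.20 points, against switching. Exchanging the two rates gives +0.20.

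**4. How many subjects.** The size of the efficacy set is not stated. Taking 342 × 0.85 = 290.7, or about 145 per arm, as a stand-in, 1-5% is 0.01 × 145 = 1.45 to 0.05 × 145 = 7.25, so about 1 to 7 subjects per arm.

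**The case against.** The strongest reply is that the plan already shows PASI percent improvement without LOCF. SAP 9.6.2.2 refits the models on observed data in two analysis sets, so for PASI the question is largely which result is labelled the main one. That stands, and it limits the point.

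It does not extend to the BSA model. SAP 9.6.3 gives observed-data BSA summaries at week 30, but only descriptive ones. Protocol 9.5.4.1 says that BSA will be handled much like PASI, which might be read as implying the repeat. The SAP does not carry it through, since SAP 9.6.2.2 refers only to the models of SAP 9.6.2.1.

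Two stronger readings are tempting, and the documents support neither:
- *LOCF always favours similarity.* It shrinks a difference only if one arises after week 20. With no difference and equal missingness there is no pull. If the week 20 difference were the larger, LOCF would move the estimate away from zero. Unequal missingness can push it either way.
- *The carried value is a pure reference-product outcome.* By week 20 the switching arm had been through two switches, and about 19% of residual drug is still ABP 501 under the decay assumption above.

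It is also fair to say that few subjects can be affected. To be imputed, a subject must have received every dose through week 28 and then lack the assessment two weeks later. Finally, LOCF is prespecified in the protocol, so replacing it is a documented departure and more than an edit to the SAP.

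**Conclusion.** The point holds as a small, avoidable weakness. The schedule, the dosing order and the LOCF definition together mean that a missing week 30 PASI or BSA score is normally replaced by one that cannot contain the effect of the third switch. That much follows from the documents alone.

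The size does not. The 0.05 to 0.5 point range rests on an assumed 1-5% missing, an assumed 5-10 point difference arising after week 20, and missingness unrelated to outcome. The understatement of uncertainty from treating carried values as observed follows from the method, but it was not quantified and should be slight at these rates.

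A reader might infer that the interchangeability conclusion is at risk. It is not: that conclusion rests on the PK ratios for AUCtau and Cmax, for which SAP 8.3 allows no imputation. PASI percent improvement is a secondary endpoint and BSA change another endpoint, and neither has a margin. The responder endpoints do not use LOCF. This is a worthwhile improvement and should not hold up the plan.

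**What to change.** In SAP 9.6.2.1 and 9.6.3:
- Make the main week 30 analysis of PASI percent improvement and BSA change the same ANCOVA after multiple imputation within arm. Impute from the day 1, week 12, week 16 and week 20 values and that arm's observed week 30 values. This assumes missingness at random given those values, and it lets the observed week 30 scores on the final ABP 501 block inform the imputed ones.
- Keep LOCF as a sensitivity analysis.
- Add an observed-data repeat of the week 30 BSA model, matching what SAP 9.6.2.2 provides for PASI.
- Record the departure from Protocol 9.5.2.2 in SAP Section 10, which already documents a change of analysis set made without a protocol amendment.

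Merely forbidding a value recorded before the week 20 dose from being carried to week 30 would add little for PASI. With no scheduled assessment in between, that rule reduces to the observed-data analysis already planned.

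The cost is SAP text, a standard imputation step, slightly wider intervals and a little more programming. No new data are needed. The change should be made before unblinding.

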3.1 Study Design

This is a randomized, double-blinded, phase 3 study in adult subjects with moderate to severe plaque psoriasis. This study is planned to be conducted globally at study centers including but not limited to North America and Europe.

The total duration of study participation for each subject will be about 36 weeks, with up to 4 weeks for screening and approximately 32 weeks after the first investigational product administration.

Subjects will receive an initial 6 doses of Humira on week 1 (day 1) mg loading dose), 1 week later on week 2 mg), then 2 weeks later on week 4, week 6, week 8, and week 10 mg), administered subcutaneously (SC). At week 12, subjects will be randomized to either the continued use group or switching group in a 1:1 ratio, stratified by geographic region and prior biologic use at baseline (week 1/day 1, yes vs. no). Subjects in the continued use group will stay on Humira Q2W with last dose at week 28 and subjects in the switching group will switch to ABP 501 Q2W at week 12 (dosed week 12 and week 14), then back to Humira Q2W at week 16 (dosed week 16 and week 18), and again to ABP 501 Q2W at week 20, (dosed week 20, week 22, week 24, week 26, and last dose at week 28).

At Week 12, efficacy assessments will be conducted including evaluation of PASI.

Protocol Number: 20200497

Date: 10FEB2023 Page 11 of 36

Subjects who do not achieve a PASI 50 response or better improvement at Week 12 are considered as non-responders and will not be randomized at Week 12; these subjects will complete End of Study (EOS) procedures at Week 12. The Lead-in Period will occur from day 1 until prior to randomization at Week 12. Those unable to complete the Week 12 visit will be discontinued from the study. All enrolled subjects not randomized at Week 12 will be considered lead-in failures and the lead-in failure reason will be documented.

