4.1 Planned Covariates

Unless stated otherwise, the stratification factors (prior biologic use for psoriasis ["yes" versus "no"] at baseline [week 1], and geographic region) will be included as covariates in the statistical models for the PK and efficacy analyses. In addition, weight and PK trough concentration at the end of the Lead-in Period (week 12) will be included as

Protocol Number: 20200497

Date: 10FEB2023 Page 12 of 36

covariates in the statistical model for the primary PK endpoints. For continuous efficacy endpoints (e.g. PASI percent improvement from baseline, Body Surface Area (BSA) change from baseline), in addition to the stratification factors, the corresponding baseline scores will also be included as covariates in models.

Covariate values may be discordant if collected via case report form (CRF) and Interactive Web/Voice Response System (IXRS). Analyses that are intended to evaluate the treatment effect and include stratification variables as covariates in the model will be based on the CRF stratification values, regardless of the subject's IXRS stratification values, to provide unbiased estimates of the effects of treatment and stratification variables without loss of efficiency (Ke et al, 2017).

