5.1 General

Actual Treatment Received During Lead-in Period

If a subject received any dose of ABP 501 during the Lead-in Period, the actual treatment for the subject is defined as ABP 501. Otherwise, the actual treatment for the subject is defined as Humira.

Actual Treatment Received During Post-randomization Period

For a subject randomized to switching group or continued use group and receiving all assigned treatments, the actual treatment received is defined as the switching group or the continued use group. Subjects randomized to the switching group that deviate from the switching regimen will be analyzed in a separate group and their actual treatment will be labeled "Deviated from Switching Regimen". Similarly, subjects randomized to the continued use group and deviate from this treatment regimen will be in actual treatment group labeled "Deviated from Continued use Regimen".

Baseline

Unless stated otherwise, the baseline of the study is defined as the last non-missing assessment taken prior to the first dose of investigational product (IP) a subject received (see definition of first dose date). In cases where baseline assessments are taken on the

Protocol Number: 20200497

Date: 10FEB2023 Page 13 of 36

same day as the first dose of IP, and either no times are reported or the IP and assessment times are the same, it will be assumed that these assessments are taken prior to IP being administered.

Change from Baseline

Change from baseline is defined as (value at post-baseline visit – value at baseline).

Concomitant and Prior Medication

Prior medications are defined as medications with a stop date prior to first dose of IP the subject received (see definition of first dose date). Concomitant medications are defined as any medications ongoing at the start of IP treatment for the subject or with a start date on or after the first dose date.

Developing ADA incidence

Developing antibody incidence during the Lead-in Period is defined as the number of subjects in the Lead in Treated Set (LTS) with a negative or no antibody result at baseline and a positive antibody result post-baseline (including unscheduled visits) during the Lead-in Period divided by the number of subjects in the LTS with at least one post-baseline result during the Lead-in Period.

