9.6.2.2 Secondary Analyses

These endpoints will also be summarized descriptively by actual treatment group based on Per-protocol Efficacy Analysis Set using observed data.

Sensitivity analyses will be conducted by repeating the models in section 9.6.2.1 using observed data in the FAS according to randomized treatment groups and in the Perprotocol Efficacy Analysis Set according to the actual treatment groups.

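### The week-30 PASI and BSA ANCOVAs adjust for the day-1 value but not the week-12 value taken before randomized dosing, so two supportive 90% CIs are probably wider than necessary (minor)

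*SAP*

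**What the plan says.** - **PASI model.** SAP 9.6.2.1: the mean difference in week-30 PASI percent improvement "will be estimated from an ANCOVA model adjusting for the baseline PASI value and the stratification factors". Protocol 9.5.2.2 and 9.5.8 name the same covariates.
- **BSA model.** SAP 9.6.3: the week-30 difference in BSA change is "estimated from an ANCOVA model adjusting for the baseline BSA value and the stratification factors with missing values imputed by LOCF".
- **General rule.** SAP 4.1: for continuous efficacy endpoints, besides the strata, "the corresponding baseline scores will also be included as covariates in models". SAP 5.1 ties baseline to the first dose of study product, that is, day 1.
- **Randomization.** It takes place at week 12 and depends on the PASI measured there. SAP 3.1: "Subjects who do not achieve a PASI 50 response or better improvement at Week 12 are considered as non-responders and will not be randomized".
- **Timing.** Protocol Table 1-1 schedules PASI, sPGA and BSA at week 12, and a footnote says "ABP 501 or adalimumab will be administered after all other procedures are completed for each visit". The week-12 values therefore precede the first randomized dose.
- **Sensitivity analyses.** SAP 9.6.2.2 repeats the 9.6.2.1 models on "observed data in the FAS according to randomized treatment groups" and on observed per-protocol data. No efficacy model contains a week-12 term.
- **Contrast.** The PK models (SAP 9.5.1.1 and 9.5.2) do adjust for the week-12 trough.

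**The concern.** Day 1 lies 12 weeks before randomization, and every subject is treated in between. The week-12 value is the same measure, taken at the point of randomization. PASI must be available for everyone randomized, because entry depends on it. If week-12 response predicts week-30 response beyond the day-1 score and strata, leaving it out keeps explainable variation in the error term, including chance differences between arms in response at randomization.

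The stake is small: the width of two supportive intervals. Protocol 2.1 describes efficacy as descriptive. The only success rule (Protocol 9.2, SAP 2.2) concerns the PK ratios. The PASI 75/90/100 and sPGA response models are not part of this point.

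**Working it through.** **Is there a planned figure to reproduce?** Not for efficacy: the documents state no SD, correlation, CI width or sample size for week-30 PASI or BSA. The one stated figure is for PK, and it holds. 342 × 0.85 = 290.7, about 145 per arm; SD(log) = √ln(1 + 0.53²) = 0.4976; exact TOST power at a ratio of 1 is 97.0% per endpoint, against at least 90% stated. It has no bearing on this point.

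**Formula.** Let r be the within-arm correlation of the week-12 and week-30 values, given the day-1 value and strata. Adding the week-12 value multiplies the CI width by about √(1 − r²), which is worth 1/(1 − r²) times the sample size.

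**Break-even.** The covariate costs 1 df. With about 243 to 335 residual df it repays itself once r exceeds √(1/335) = 0.055 to √(1/243) = 0.064. If r = 0, the CI is about 0.2% wider (n about 290).

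**Inputs for r, all assumed.** The PASI 50 rule and the 100% ceiling restrict the range and lower r, so this was simulated:
- bivariate normal week-12 and week-30 improvement, with underlying (latent) correlation 0.3, 0.5 or 0.7;
- week-12 mean 80, 85 or 90, with the SD set so that 5%, 10% or 17% fall below 50. The 17% is the all-cause lead-in failure rate in SAP 3.2, so an upper bound for non-response;
- week-30 mean 85, 90 or 95 (not below the week-12 mean), SD 15 or 20;
- both values capped at 100, and subjects below 50 at week 12 removed;
- 48 combinations per correlation, 1.5 million draws each.

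| Latent r | Observed r | CI narrowing, 1 − √(1 − r²) | Equivalent sample size |
|---|---|---|---|
| 0.3 | 0.176–0.256 | 1.6–3.3% | 1.03–1.07 × |
| 0.5 | 0.308–0.436 | 4.9–10.0% | 1.10–1.23 × |
| 0.7 | 0.473–0.634 | 11.9–22.7% | 1.29–1.67 × |

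Example: observed r = 0.436 gives 1 − √(1 − 0.190) = 10.0%. The smallest gain is at means 90/95, 17% below the cut and SD 20; the largest is at means 80/85, 5% below the cut and SD 15. Fitting the ANCOVA with treatment, day-1 PASI and two strata gave nearly the same narrowing: 1.6%, 4.9% and 12.1% at 90/95, 17%, SD 20; 3.2%, 9.7% and 21.9% at 80/85, 5%, SD 20. Ignoring the entry rule and ceiling would overstate the gain, at about 4% to 28% for r of 0.3 to 0.7.

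**In points.** Half-width = 1.645 × SD × √(4/n). The size of the efficacy set is not given. With an assumed SD of 15, n = 250 gives 3.12 and n = 342 gives 2.67. At latent r = 0.5 the reduction is 2.67 × 0.0486 = 0.13 to 3.12 × 0.100 = 0.31.

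**LOCF.** SAP 5.1: "missing post-baseline data will be imputed by carrying forward the last non-missing post-baseline value for that endpoint". A subject with no PASI at weeks 16, 20 and 30 would have the week-12 value as both covariate and outcome. If 5% of week-30 values arose this way, the narrowing would look larger than it is: 4.9% becomes 6.4%, and 9.6% becomes 10.8% (latent r = 0.5). Across the settings tried, the inflation is 0.9–1.9 percentage points.

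**The case against.** The strongest reply is that this is a preference. The planned model is complete and prespecified, protocol and SAP agree on the PASI covariates, no bias or error-rate problem follows, and there is no efficacy margin for a narrower CI to meet. The gain rests on an assumed correlation and runs from negligible to useful. Using the week-12 trough in the confirmatory PK model does not oblige the efficacy models to follow. The change also brings LOCF overlap and a departure from covariates the protocol names.

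Most of this stands, and it is why the point is minor. It does not remove it: the data are already scheduled, and the cost if the covariate proves useless is about 0.2% of CI width.

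Two details deserve an answer:
- **SD.** The 15 points is a value before capping. Using the SDs after selection and capping (9.2–15.6 at latent r = 0.5), half-widths are 1.6–3.2 points and the gain 0.08–0.31, essentially the same.
- **Pre-dose timing.** Visit procedure largely secures it, and the week-14 dose is nominally day 92 (78 + 14), outside the week-12 window of days 57–91. But SAP 5.1 takes the assessment closest to day 78, and the later one in a tie. An unscheduled assessment on day 80 would displace a visit on day 75. The post-dose exclusion covers laboratory values only.

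**Conclusion.** The point holds as a minor improvement. The week-12 value is measured before randomized dosing and appears in no efficacy model. Using it would probably narrow the week-30 PASI 90% CI, by about 5–10% at a latent correlation of 0.5 and by 1.6% to 22.7% over 0.3 to 0.7. These figures depend on assumed correlations, means, SDs and non-response rates. No figure is claimed for BSA. The planned estimates are not wrong, and no decision rule or PK conclusion changes.

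A separate discrepancy, not counted in this rating: Protocol 9.5.3 plans changes from week 12 for post-randomization laboratory values and vital signs. SAP 9.7.2 and 9.7.3 use change from baseline, keeping week 12 only for laboratory toxicity shift tables. SAP Section 10 does not declare this.

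**What to change.** Before unblinding:

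1. Add week-12 PASI percent improvement to the PASI ANCOVA and week-12 BSA to the BSA ANCOVA, keeping the day-1 value and strata.
2. Define the week-12 value as the last assessment before the first post-randomization dose, and state how a missing week-12 BSA is handled.
3. Report how many week-30 values are carried from week 12. These should be few, since the efficacy set requires all assigned doses (SAP 6.5). Compare with the observed-data PASI analysis already planned, and add an observed-data run of the BSA ANCOVA, which has none.
4. List the change in SAP Section 10, because the protocol names the PASI covariates.
5. Leave the PASI 75/90/100 and sPGA models as planned. A logistic model with a standardized risk difference is an optional sensitivity analysis.

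The cost is 1 df per model, one definition with its missing-data rule, a count of carried values, one extra run and a Section 10 entry. No new data are needed.

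For the separate discrepancy, restore change from week 12 for post-randomization laboratory values and vital signs, or declare the departure in Section 10.
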